#### Mechanical ventilation:

- 1. Ventilation free days
- 2. Incidence and duration of new mechanical ventilation use during the trial

#### Hospitalisation:

Duration of hospitalisation (days)

Mortality:

29 day mortality

## Safety of the intervention:

- 1. Cumulative incidence of serious adverse events (SAEs) from day 1 to 29.
- 2. Discontinuation or temporary suspension of treatment from days 1 to 28.

#### Quality of life

1. EQ-5D-5L at day 29

## 4.3 Derived variables

The primary endpoint is an assessment of the clinical status on a given trial day using a 7-point ordinal scale. Each day, the worse score for will be recorded. The scale is as follows:

- 1. Not hospitalised, no limitations on activities
- 2. Not hospitalised, limitation on activities;
- 3. Hospitalised, not requiring supplemental oxygen;
- 4. Hospitalised, requiring supplemental oxygen;
- 5. Hospitalised, on non-invasive ventilation or high flow oxygen devices;
- 6. Hospitalised, on invasive mechanical ventilation or ECMO;
- 7. Death.

#### The NEWS score is based on 7 clinical parameters:

- 1. Respiration rate (per minute)
- 2. SpO2 Scale 1(%)
- 3. Air or Oxygen
- 4. Systolic blood pressure (mmHg)
- 5. Pulse (per minute)
- 6. Consciousness
- 7. Temperature (°C)

## 5 Study Methods

## 5.1 General Study Design and Plan

(ICH E3;9)

This is a multi-centre, randomised, double blind, placebo controlled, parallel group trial with two treatment arms, with 400 participants planned to be randomised

The two treatment arms are as follows:

[figure not shown]
- 1. Brensocatib 25mg once daily for 28 days
- 2. Placebo once daily for 28 days

Following trial completion or discontinuation, participants should be continued on standard of care.

Randomisation will be stratified by

- 1. Site
- 2. Age: <65 years/≥65 years

The proposed primary outcome assessed on a 7-point ordinal scale at day 28.

## 5.2 Inclusion-Exclusion Criteria and General Study Population

It is likely that the assessments to confirm eligibility will be carried out by the clinical team during routine care of patients being assessed for COVID-19. Where these assessments have been carried out by the clinical team the most recent of these results will be used to prevent duplication and further exposure of the trial staff to patients with COVID-19.

#### 5.2.1 Inclusion criteria

- Male or female
- $\geq 16$  years of age
- SARS-CoV-2 infection (clinically suspected+ or laboratory confirmed\*).
- Admitted to hospital as in-patient less than 96 hours prior to randomisation^
- Illness of any duration, and at least one of the following:
  - Radiographic infiltrates by imaging (e.g. chest x-ray, computed tomography (CT) scan)

OR

- Evidence of rales/crackles on physical examination OR
- Peripheral capillary oxygen saturation (SpO2) ≤94% on room air prior to randomization

OR

Requiring supplemental oxygen.
 OR

- Lymphocyte count <1 x 109 cells per litre (L)
- Participant (or legally authorized representative) provides written informed consent
- Able to take oral medication
- Participant (or legally authorised representative) understands and agrees to comply with planned trial procedures.

\*Laboratory-confirmed: SARS-CoV-2 infection as determined by polymerase chain reaction (PCR), or other commercial or public health assay in any specimen < 96 hours prior to randomization.

+Clinically suspected: in general, SARS-CoV-2 infection should be suspected when a patient presents with (i) typical symptoms (e.g. influenza-like illness with fever and muscle pain, or respiratory illness with cough and shortness of breath); and (ii) compatible chest X-ray SAP version 2 STOP COVID-19

05-04-2021

Page 10 of 46

findings (consolidation or ground-glass shadowing); and (iii) alternative causes have been considered unlikely or excluded (e.g. heart failure, influenza). However, the diagnosis remains a clinical one based on the opinion of the managing doctor

^Where a patient has been admitted to hospital for a non COVID-19 reason and develops COVID-19 symptoms whilst an in-patient, randomisation may occur up to 96 hours from onset of symptoms.

#### 5.2.2 Exclusion criteria

- Alanine aminotransferase (ALT) and/or aspartate aminotransferase (AST) > 5
  times the upper limit of normal, result within 72 hours of randomization (the
  result closest to randomization should be used if several results are available).
- History of severe liver disease
- Stage 4 severe chronic kidney disease or requiring dialysis (i.e. eGFR < 30), result within 72 hours of randomization (the result closest to randomization should be used if several results are available)
- Absolute neutrophil count less than  $1.0 \times 10^9$  cells per L within 72 hours of randomization (the result closest to randomization should be used if several results are available)
- Current treatments with potent Cyp3A4 inducers/inhibitors (e.g Itraconazole, Ketoconazole, diltiazem, verapamil, phenytoin or rifampicin)
- HIV treatments current treatment with protease/integrase inhibitors or nonnucleoside reverse transcriptase inhibitors\*
- Pregnant or breast feeding.
- Anticipated transfer to another hospital which is not a trial site within 24 hours.
- Allergy to Brensocatib
- Use of any investigational drug within five times of the elimination half-life after the last trial dose or within 30 days, whichever is longer. Co-enrolment with COVID-19 trials is allowed as per co-enrolment agreements and/or individual decision by the CI.

Women of child-bearing potential must be willing to have pregnancy testing prior to trial entry.

\*The Liverpool HIV checker (https://www.hiv-druginteractions.org/checker) should be used to check for any HIV drug interactions. Simvastatin could be used as a surrogate for Brensocatib as it metabolised similarly by CYP 3A4 pathway.

#### 5.2.3 Co-enrolment

Co-enrolment into COVID-19 CTIMPs will be described in individual agreements between STOP-COVID19 and other trials. These agreements will be made available to recruiting sites. Where agreements are not in place for specific trials the site should contact the CI and co-enrolment will be decided on an individual participant basis. This decision will be documented in the participant's medical record.

Co-enrolment into COVID-19 non-CTIMP intervention trials will be allowed.

Co-enrolment to other non-COVID-19 Clinical Trials of Investigational Medicinal Product (CTIMPs) will not be allowed.

Enrolment in observational trials or studies will be allowed.

Enrolment in observational trials will not be an exclusion to participation.

Co-enrolment in another CTIMP is not acceptable

## 5.3 Randomisation and Blinding

Participants will be allocated to receive either Brensocatib (25mg once daily for 28 days) or placebo in addition to standard of care. Randomisation will be 1:1 intervention:placebo. Randomisation will be stratified by site and age: <65 years/≥65 years. Randomisation will be done centrally using a web-based validated randomisation program provided by Tayside Clinical Trials Unit. The trial is doubled-blind, participants and trial staff are blind to allocation, unblinding will take place after database lockdown. Emergency unblinding procedures are described in section 7.6 of the protocol.

# 5.4 Study Variables

Table 1: Study variables

	Screeningd	Randomizationd			Follow-up	Follow-up	Follow-up	Unscheduled
					Assessment	assessments	Assessments	Assessments
					S			
	Day 0 or 1	Day 1	Daily	Days 3, 5 &11	Day 8c	Day 15 c	Day 29 c	As Required in
Timeline		Up to 24 hours	whilst	С	(telephone	(telephone	(telephone	the event of AE
Timeline		after screening	hospitalise	(telephone call	call if at	call if at	call if at	
			d	if at home)	home)	home)	homeb)	
Informed Consent	X							
Inclusion/Exclusion	Х	Х						
Criteria Check	^	^						
Medical History	X							
Record Concomitant	Х	Х			Х	Х	X	Х
Medications	^	^			^	^	^	^
Check Vital Signs*^	X	X			X∞	X∞	X∞	X
ECG*	X							
Full blood count*+	X			X∞	X∞	X∞	X∞	
Urea and electrolytes*+	X			X∞	X∞	X∞	X∞	
Liver function tests*+	Х			X∞	X∞	X∞	X∞	
SARS CoV-2 PCR*	Х							
Record SARS CoV-2 PCR								
results, only if done for				X	X	X	X	
clinical reasons								

	Screeningd	Randomizationd			Follow-up	Follow-up	Follow-up	Unscheduled
					Assessment	assessments	Assessments	Assessments
					S			
	Day 0 or 1	Day 1	Daily	Days 3, 5 &11	Day 8 c	Day 15 c	Day 29 c	As Required in
Timeline		Up to 24 hours	whilst	С	(telephone	(telephone	(telephone	the event of AE
Timeline		after screening	hospitalise	(telephone call	call if at	call if at	call if at	
			d	if at home)	home)	home)	home b )	
Nasal swab for SARS CoV-						X∞	X	
2 PCR* (Tayside only)						X	^	
Research Blood Sample *								
(Tayside and Sheffield		X			X∞	X∞	X	X
only)								
Sputum sample for								
storage if available*+		X			X∞	X∞	X	
(Tayside only)								
Endotracheal aspirate								
sample for storage if					X∞	X∞	X∞	
available*+a (Tayside only)								
Clinical status on 7 point	Х	Х	Х	х	Х	Х	X	х
scale	^	^	^	^	^	^	^	^
NEWS recording*	X	X	X	X∞	X∞	X∞	X∞	
EQ-5D questionnaire							X	
Record supplemental	Х	Х			V	V	V	V
oxygen*	^	^			X∞	X∞	X∞	X
Record CT scan results,								
only if done for clinical	X	X	Χ	X∞	X∞	X∞	X∞	Χ∞
reasons								

	Screeningd	Randomizationd			Follow-up	Follow-up	Follow-up	Unscheduled
					Assessment	assessments	Assessments	Assessments
					S			
	Day 0 or 1	Day 1	Daily	Days 3, 5 &11	Day 8 c	Day 15 c	Day 29 c	As Required in
Timeline		Up to 24 hours	whilst	С	(telephone	(telephone	(telephone	the event of AE
Timeline		after screening	hospitalise	(telephone call	call if at	call if at	call if at	
			d	if at home)	home)	home)	homeb)	
Pregnancy Testing (urine	Х							
or blood) If Applicable	^							
Record Adverse Events		X	X	X	X	X	X	X
Randomisation		X						
Dispense Trial Drugs		X						
Drug Return And							Х	
Compliance Check							^	

^ Vital Signs: Blood Pressure, pulse, temperature, oxygen saturation

\*indicates procedures that will be performed by the clinical team as part of routine care but results will be recorded and included in the eCRF.

If not performed by the clinical team, but clinically indicated, the research team may assist in this being performed but all processes will avoid duplication and exposure to potentially infected participants.

+Excess biological samples that are being taken for clinical reasons may be stored for future use if no longer required for clinical purposes (Tayside only).

<sup>a For those participants who are intubated.

∞These assessments will not be completed if the participant has been discharged from hospital.

<sup>b For the Tayside and Sheffield site only, the day 29 assessments will be carried out face-to-face either at a NHS facility or at the participant's home. Home visits will only be carried out if no one in the household has symptoms of COVID-19.

 $^{c}$ Research blood samples (Tayside and Sheffield only) and, once discharged, assessments may be completed within +/-1 day

dScreening and randomisation may occur on the same day if all eligibility criteria are met. Day of first dose of IMP will be considered as day 1 for the calculation of follow up assessments.

## 6 Sample Size

(ICH E3; 9.7.2. ICH E9; 3.5)

In accordance with the WHO multicentre adaptive trial design recommendations, this trial is intended to allow for adaptation of blinded confirmation or modification of the primary endpoint.

Prior to the commencement of the trial, we took the anticipated WHO scenario and the odds ratio of 2 which required enrolment of 272 participants. Allowing for a potential loss to follow–up of 9% (27 participants) this meant we will required 300 participants (150 per arm) to achieve 85% power at 5% significance. This was subsequently reviewed as part of a pre–specified blinded sample size re–evaluation by an independent statistician. The results of this re–evaluation, using data for the primary endpoint available in December 2020 found that 300 patients enrolled would provide approximately 88% power to detect an odds ratio of 2.0. This, along with the results of other COVID–19 trials were reviewed by the Trial Steering Committee (TSC) and DMC who noted that other COVID–19 therapeutics had achieved odds ratios lower than 2.0 in the majority of cases. Based on this, the TSC and DMC recommended targeting an odds ratio of 1.75. At least 80% power for an odds ratio of 1.75 requires enrolment of a minimum of 360 patients with 400 patients provided approximately 85% power. A final sample size of 400 subjects was therefore recommended by the TSC and subsequently approved by the DMC in December 2020 (Appendix 1).

#### 7 General Considerations

## 7.1 Timing of Analyses

The final analysis will be conducted following last patient last visit assuming that at least 400 patients have been enrolled.

## 7.2 Analysis Populations

(ICH E3; 9.7.1, 11.4.2.5. ICH E9; 5.2)

## 7.2.1 Full Analysis Population

The primary analysis will be based on the intention-to-treat principle, which will include all participants who are randomised and received at least one dose of randomised therapy.

## 7.2.2 Per Protocol Population

Per-protocol (PP) analyses restricted to participants who completed the trial or died without a major protocol violation/deviation.

#### 7.2.3 Preliminary analysis population

Includes all subjects in the full analysis population with complete endpoint data available as of 5/4/2021 for preliminary analysis on an unlocked database.

#### 7.2.4 Safety Population

Safety analyses will be based a modified intent-to-treat population consisting of all participants who were randomised and received at least one dose of randomised therapy.

## 7.3 Covariates and Subgroups

(ICH E3; 9.7.1, 11.4.2.1. ICH E9; 5.7)

#### 7.3.1 Covariates

The primary analysis will be adjusted for the stratification variables (site and age). Baseline ordinal scale will be included if considered necessary.

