#### 7.3.2 Subgroups

The primary endpoint will be analysed for the following participant subgroups:

1. Age (years): (a) <65 years and (b)  $\ge 65$ 

- 2. Sex at birth: (a) Male and (b) Female
- 3. Symptom duration (days): (a) <10 and (b)  $\ge 10$
- 4. Baseline 7-point ordinal scale: (a) 3, (b) 4 and (c) 5
- 5. Co-enrolment into RECOVERY: (a) Yes and (b) No
- 6. Co-treatment with dexamethasone: (a) Yes and (b) No (if a meaningful number if patients did not receive dexamethasone)

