## 7.6 Preliminary analysis

An analysis for preliminary efficacy and safety will be performed on an unlocked database using the full analysis population. The preliminary analysis will focus on the primary endpoints and a limited number of key secondary endpoints plus safety. The endpoints to be evaluated in the preliminary analysis are as follows:

Primary endpoint: Clinical Status on the WHO ordinal scale at day 29

Key secondary endpoints: Time to improvement on the ordinal scale, proportion of patients requiring mechanical ventilation, mortality, duration of hospitalization

Safety: Proportion of patients with one or more adverse events, proportion of patients with serious adverse events

Virologic efficacy of Brensocatib: Neutrophil elastase measurement in blood by treatment arm.

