## 7.7 Multi-centre Studies

(ICH E3;9.7.1, 11.4.2.4. ICH E9; 3.2)

This is a multi-centre trial recruiting from 15 NHS Trusts/Boards within UK, if required to fulfil recruitment more NHS Trusts/Boards will be added.

Centre will be treated as random effect in the mixed ordinal logistic regression model and analysis of secondary outcomes.

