#### 8.3.1 Other Baseline Characteristics

The following baseline disease characteristics will be summarized by treatment group and overall using descriptive statistics:

- Clinical status (7-point ordinal scale)
- Severity of illness
- Participants with confirmed SARS-CoV-2 PCR test and those treated as clinically suspected who never had a positive swab

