## 9 Efficacy Analyses

## 9.1 Primary Efficacy Analysis

The primary endpoint will be analysed using a mixed ordinal logistic regression, assuming proportional odds ratios adjusted for age and sites as a random effect. The odds ratio, 95% confidence interval and p-value for comparing treatments will be provided. The assumption of odds proportionality will be assessed using Brant Test of Parallel Regression Assumption. If the test indicate that proportional odds assumption is violated, the model will be run as a generalised ordered logistic model.

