## Table 2: Demographic

Variable	Brensocatib	Placebo
	N =	N =
Age (mean SD)		
Gender - n (%)		
Male		
Female		
Ethnicity - n (%)		
English/ Welsh/ Scottish/ Northern Irish/ British		
Irish		
Gypsy or Irish Traveller		
Any other White background		
White and Black Caribbean		
White and Black African		
White and Asian		
Any other Mixed/ Multiple ethnic background		
Indian		
Pakistani		
Bangladeshi		
Chinese		
Any other Asian background		
African		
Caribbean		
Any other Black/ African/ Caribbean background		
Arab		

Any other ethnic group

Unknown

Living status - n (%)

Own home (on own or with others)

Sheltered housing

Care home (nursing or residential)

Prison

Other

Comorbidities

- a. Chronic Neutropenia
- b. Chronic cardiac disease, including congenital heart disease
- c. Hypertension
- d. COPD
- e. Chronic pulmonary disease (not COPD or asthma)
- f. Asthma (physician diagnosed)
- g. Chronic kidney disease (eGFR less than 44 ml/min, on dialysis or previous transplant)
- h. Moderate or severe liver disease
- i. Mild liver disease
- j. Chronic neurological disorder
- k. Malignant neoplasm
- I. Chronic hematologic disease
- m. AIDS / HIV
- n. Obesity
- o. Diabetes with complications
- p. Diabetes without complications
- q. Rheumatologic disorder
- r. Dementia
- s. Malnutrition

Table 3: Severity of the patient population

		Brensocatib	Placebo
SAP version 2 STOP COVID-19	05-04-2021		Page 32 of 46

N = N =

Radiographic infiltrates by imaging (e.g. chest x-ray,

computed tomography (CT) scan)

Evidence of rales/crackles on physical examination

Peripheral capillary oxygen saturation (SpO2) less

than or equal to 94% on room air prior to

randomization

Requiring supplemental oxygen

Lymphocyte count less than 1 x 10^9 cells per litre

(L)

Table 4: SARS-COV—2 PCR test

	Brensocatib	Placebo
	N =	N =
Confirmed positive SARS CoV-2 PCR test		
Clinically suspected without a positive		
swab		

Table 5: Clinical status at randomisation

Brensocatib	Placebo
N =	N =

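### The primary model's covariate set is not uniquely fixed: baseline 7-point status is optional in SAP 7.3.1 and absent from SAP 9.1

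*SAP*

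**What the plan says.** - **SAP 7.3.1 (Covariates)** names site and age as adjustment variables for the primary analysis and adds: "Baseline ordinal scale will be included if considered necessary". It does not say what would make the term necessary, who decides, or when.
- **SAP 9.1 (Primary Efficacy Analysis)** specifies a mixed ordinal logistic regression "assuming proportional odds ratios adjusted for age and sites as a random effect". It has no baseline term.
- **SAP 7.7 (Multi-centre Studies)** fixes only the centre term: "Centre will be treated as random effect in the mixed ordinal logistic regression model and analysis of secondary outcomes".
- **Protocol 10.4 (Adjusted analysis)** defers to the SAP and adds no rule.
- Baseline status is used elsewhere. It is a subgroup factor in SAP 7.3.2 ("Baseline 7-point ordinal scale: (a) 3, (b) 4 and (c) 5"), a baseline descriptive in SAP 8.3.1, and a table shell in SAP 16 ("Table 5: Clinical status at randomisation").
- **SAP 7.6 (Preliminary analysis)** states: "An analysis for preliminary efficacy and safety will be performed on an unlocked database using the full analysis population". The endpoints listed there include day-29 clinical status. SAP 7.2.3 limits this population to participants with "complete endpoint data available as of 5/4/2021 for preliminary analysis on an unlocked database". The page footer of SAP version 2 carries the date 05-04-2021.

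**The concern.** A confirmatory analysis needs one model that can be written down before the arms are compared. Here a reader who follows 9.1 fits one model, and a reader who uses the option in 7.3.1 may fit another. Both are legitimate, but they can fall on different sides of 0.05. Because the odds ratio is non-collapsible, they also estimate slightly different quantities. So both the reported p-value and the meaning of the reported odds ratio are open.

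The timing adds weight. The SAP version that leaves the choice open bears the same date as the data cut for an analysis of the primary endpoint on an unlocked database, and no section requires the covariate decision to come first.

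**Working it through.** **1. The plan's own figures.** Inputs are the SAP Table 2 control proportions (2, 1, 2, 7, 8, 38 and 42%, worst to best), 1:1 allocation and two-sided 5% significance. For ordered categories,

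N = 12 (z₀.₉₇₅ + z_power)² / [(ln OR)² (1 − Σ p̄³)],

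where p̄ is the mean of the two arms' proportions in each category.

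For OR 1.75, (ln OR)² = 0.3132 and Σ p̄³ = 0.1599.
- N for 85% power = 12 × (1.960 + 1.036)² / (0.3132 × 0.8401) = 409.5 (SAP Table 3: 412).
- Power at N = 400 = Φ(√(400 × 0.3132 × 0.8401 / 12) − 1.960) = Φ(2.961 − 1.960) = 84.2% (stated: about 85%).
- Power at N = 360 = 80.2% (stated: at least 80%).
- Power at N = 300 for OR 2.0 = 88.5% (stated: about 88%).

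The plan reproduces. The formula has no covariate term, so the open choice does not touch the sample size.

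**2. What the open choice is worth.** The documents give neither the baseline mix nor its prognostic strength, so both are assumed. Simulation A uses the planned mixed model:
- 400 patients in 15 sites of unequal size, with site SD 0.4 on the log-odds scale;
- permuted blocks of 4 within site and age group;
- half of patients aged 65 or over, with odds of worse outcome ×2 and of worse baseline ×1.3 in that group;
- baseline categories 3/4/5 at 25/60/15% or 10/60/30%;
- control outcomes calibrated to Table 2, and unadjusted OR 1.75;
- Wald tests at two-sided 5%, 4,000 replicates per setting.

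| Odds of worse outcome per baseline category | Power, age + site | Power, plus baseline | Gain (points) | Models disagree on p<0.05 | Type I error if the significant one is reported |
|---|---|---|---|---|---|
| ×1.5 | 87.0–87.6% | 87.3–87.5% | −0.3 to +0.5 | 2.5–2.7% | 5.5–5.9% |
| ×2.0 | 86.2–86.6% | 88.3–88.6% | +2.0 to +2.1 | 4.0–4.1% | 5.5–6.4% |
| ×2.7 | 87.6–87.8% | 90.3–90.4% | +2.6 to +2.7 | 4.8–5.3% | 6.5–6.8% |

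The Monte Carlo standard error is about 0.5 points for power and 0.3 to 0.4 for the paired gain and the null rates. Fixed in advance, each model holds its level: 4.7–5.2% without baseline status and 4.7–5.6% with it. The median estimated odds ratio is about 1.82 for age and site, and 1.84, 1.86–1.87 and 1.90–1.91 with baseline status at the three strengths.

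**3. Sensitivity to the assumptions.** Simulation B has no site effect, 40% aged 65 or over, baseline 25/60/15%, and 1.75 as the conditional rather than the unadjusted odds ratio. At ×1.5, ×2.5 and ×4.0 per category:
- power without and with baseline is 82.3% and 82.5%, 77.5% and 81.3%, 72.8% and 81.5%;
- the models disagree in 2.8%, 7.9% and 12.3% of trials;
- the pick-the-better error is 6.1%, 6.5% and 7.2%, against 4.8–5.4% for either model fixed in advance.

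The gains are larger partly because fixing the conditional odds ratio shrinks the effect seen by the model without baseline. Simulation A is closer to the design, whose 1.75 enters a formula without covariates.

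**4. Which baseline value.** SAP 4.2 equates baseline with day 1 for change on this scale. Protocol 8.7 makes day 1 the day of first dose, which can be the day after randomisation. Protocol 7.8 and SAP 4.3 record the worst score of each day. A day-1 score can therefore include hours after the first dose. Status is also scheduled at screening and at randomisation (protocol Appendix 4, SAP 5.4).

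**The case against.** **A default exists.** SAP 9.1 is the operative section, and it writes exactly the site-and-age model that 7.3.1 fixes. Deleting the optional sentence would cure the ambiguity without adding a covariate. That is correct. Making baseline status mandatory is a judgement that a small, assumption-dependent gain is worth having from a value already recorded; at ×1.5 there is nothing to gain. The objection does not remove the defect, because 7.3.1 governs the same analysis and expressly permits a different model.

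**The size is assumed.** This also stands. The two simulations agree in direction but not in magnitude, and at ×1.5 the pick-the-better error in simulation A overlaps the single-model null rate within Monte Carlo error. The figures are illustrative.

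**Stronger readings that the documents do not support:**
- *The type I error is inflated.* This would require choosing the model after seeing both results. No section says this will be done, so the figures are a ceiling.
- *The arms were compared before lock.* SAP 7.6 mentions treatment arm only for neutrophil elastase. A by-arm analysis of the primary endpoint is a reasonable inference but is not stated. It would conflict with SAP 5.3 and protocol 7.5, which place unblinding after lock. That conflict is a separate issue.
- *The sample size or the 9.1 model is wrong.* Step 1 of the working shows that the sample size reproduces, and the 9.1 model holds its error rate.
- *Fixing the covariate removes all model choice.* It does not. SAP 9.1 also switches to a generalised ordered logistic model if the Brant test indicates non-proportional odds. That too is separate.

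**Conclusion.** The point holds in a limited form. The primary covariate set is not uniquely prespecified: 7.3.1 leaves baseline status open and 9.1 omits it. This rests on the text alone and needs no assumption.

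The consequences are small. On assumed prognostic strength, with the unadjusted odds ratio held at 1.75, adjustment gives no detectable power gain at ×1.5 per category and about 2 to 3 points at ×2.0 to ×2.7. A choice made after seeing results would take type I error to at most about 5.5 to 7%. The sponsor should settle it, but the default analysis is sound and no stated figure changes.

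**What to change.** Delete the optional sentence and put the same model in SAP 7.3.1 and 9.1, for example: *The primary model includes treatment, age group and baseline 7-point status (categories 3, 4 and 5, any other value grouped with the nearest) as fixed effects, and site as a random effect. The odds ratio is conditional on these terms.* Report the age-and-site model as a named sensitivity analysis.

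Define baseline as the last status recorded at screening or randomisation before the first dose. Reconcile this with the day-1 baseline in SAP 4.2 and the worst-score-of-day rule, so that no post-dose status enters the covariate.

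Date the decision before any by-arm analysis. SAP version 2 carries the same date as the preliminary data cut, so that may no longer be possible. If a by-arm look has already occurred, keep the 9.1 model as primary, report the baseline-adjusted model as sensitivity, and give the dates of the look and of the covariate decision.

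**Cost.** SAP wording, plus a check that the eCRF holds a status value identifiable as pre-dose. Clinical status is scheduled at screening and randomisation, but no section guarantees a separate pre-dose reading. The odds ratio must be labelled as conditional when set beside the design value of 1.75. The 9.1 odds ratio is already conditional on age and site, and in simulation A adding baseline status moves the median from about 1.82 to between 1.84 and 1.91.
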